- Questioning about ocular and non-ocular concomitant treatments
- Review of the completion patient diary
- Questioning about IMD dose regimen compliance
- Slit lamp examination for measuring*:
 - Measurement of conjunctival hyperaemia with [REDACTED] photographic scale
 - TBUT
 - Oxford 0-15 grading scheme (corneal and conjunctival staining by fluorescein with a yellow filter),
- Schirmer test* (without anaesthesia),
- AE reporting
- Device deficiency
- Assessment of the ocular tolerance by the investigator
- Assessment of the performance by the investigator

* Examination must be performed by the same **masked investigator or delegate for selected tasks** for all visits and using the same slit lamp.

By the unmasked collaborator:

- Recording the number of returned used and unused IMD in document source (the accountability is expected for the amount of bottles) and transfer this information to masked investigator.

The next visit must be scheduled at Day 36 later (+3days)

Visit#4: Day 36 (+3days)

Visit#4 will consist of the following procedures and examinations to be done according to the following order and in each eye.

By the masked investigator (the same as the screening visit) or delegate for selected tasks (according to local requirements, the investigator may delegate tasks to collaborator).

- ✓ On paper CRF
- Questionnaire (OSDI)
- Ocular discomfort (VAS)

- ✓ On eCRF
- Questioning about ocular symptoms upon instillation questionnaire
- Questioning about ocular symptoms within the last 48 hours
- Questioning about soothing sensation 15 min after IMD instillation
- Assessment of global patient satisfaction with the use of bottle
- Assessment of global satisfaction by the patient
- Assessment of the ocular tolerance by the patient
- Questioning about ocular and non-ocular concomitant treatments
- Measurement of Far Best Corrected Visual Acuity,
- Review of the completion patient diary
- Questioning about IMD dose regimen compliance
- Slit lamp examination for measuring*:
 - Measurement of conjunctival hyperaemia with [REDACTED] photographic scale
 - TBUT
 - Oxford 0-15 grading scheme (corneal and conjunctival staining by fluorescein, with a yellow filter),
- Schirmer test* (without anaesthesia),
- AE reporting
- Device deficiency
- Assessment of the ocular tolerance by the investigator
- Assessment of the performance by the investigator
- Status of the patient

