* Examination must be performed by the same masked person for all visits and using the same slit lamp.

By the unmasked collaborator:

- Recording the number of returned used and unused IMD in source document (the accountability is expected for the amount of bottles), and transfer this information to masked investigator.

Premature discontinuation Visit during the investigation

A patient who prematurely discontinues from the investigation should have, if possible, a premature discontinuation visit. This last site visit should take place as soon as possible after the patient stops taking IMD. All follow-up procedures and examinations scheduled to be performed at the final visit should be performed at the patient's premature discontinuation visit.

If the patient is tested COVID-19 positive during the course of the study, the patient has to inform the investigator. Either the patient may continue the investigation when he/she can follow the protocol requirements safely and in accordance with the national/regional recommendations or the patient may be withdrawn from the investigation. The last site visit should take place as soon as possible after the patient stops taking IMD.

Note: Randomised patients who withdraw will not be replaced by another subject. The subject number and associated randomisation number of the withdrawn subject must not be reassigned to a different subject.

Adaptive Follow-Up of Patients Prematurely Withdrawn due to an Exceptional Circumstance (e.g. COVID-19 pandemic)

If the patient withdrew from the investigation due to an exceptional circumstance, and if an onsite visit was not authorised, a premature discontinuation visit by phone is required.

– **Premature discontinuation phone call**

- Check the IMD compliance with the patient
- Instruct the patient to stop the IMD and keep used and unused IMD for later return
- Ensure the continuity of artificial medication as per routine clinical practice
- Collect AE/Serious Adverse Event (SAE) and any changes in concomitant treatments
- Collect DD
- Plan a safety onsite visit 4 weeks later (± 7 days) and ensure that the patient understands all recommendations
- Record the phone call and all information collected in the patient medical record

Safety Follow-up visit on site¹

During the onsite follow-up visit done 4 weeks later (± 7 days) after the premature discontinuation phone call, the following procedures are required:

- Check the IMD compliance with the patient

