0 = Absent

1 = Mild, present but not disturbing

2 = Moderate, disturbing, but not limiting with daily activities

3 = Severe, very distressing and interfering with daily activities

The ocular symptoms will be assessed in global for both eyes at each visit. The value at D1 will be the baseline value.

- *Slit Lamp Examination*

- Conjunctival hyperaemia

The level of severity of conjunctival hyperaemia will be scored using the [REDACTED] photographic scale (0 to 5) in each eye.

[REDACTED]

- Tear Break-Up Time (TBUT)

The tear film stability will be measured 3 times after the instillation of fluorescein. TBUT will be rapidly assessed and expressed in seconds. The sum of the 3 measures will also be expressed in seconds.

TBUT will be measured in each eye.

- Total ocular surface staining (Oxford scale)

The total ocular staining grade using Oxford 0-15 grading scheme will be assessed by the staining in corneal area and conjunctival areas (temporal and nasal) by fluorescein with a yellow filter.

The Global Score (sum of score reported for each area: corneal + conjunctival) for each eye will be recorded.

- *Schirmer Test*

The Schirmer test will be performed without anaesthesia.

The test should be done **without touching directly the strip with the finger** to avoid contamination of skin lipids.

The strip should be placed in the temporal part to avoid any contact with the cornea. The patient should keep the eyes closed. Values should be measured just at the end of the 5 minutes.

The Schirmer test will be measured in mm/5 min in each eye.

- *Performance Assessment by the investigator*

The investigator has to answer to the following question at the end of the patient examination:

“Do you consider the IMD performance as:

- Very satisfactory
- Satisfactory
- Not very satisfactory
- Unsatisfactory”

- *Patient satisfaction*

- Global satisfaction assessment by the patient

The patient has to answer to the questionnaire in local language.

“In a scale from 0 to 10, where 0 is COMPLETELY UNSATISFIED and 10 is COMPLETELY SATISFIED, indicate the number which corresponds the best to your overall satisfaction”

- Global patient Satisfaction assessment with the use of the bottle

The patient has to answer to this question in local language.

“Are you satisfied with the use of the bottle?”

- Very satisfactory
- Satisfactory
- Not very satisfactory
- Unsatisfactory”

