6.4.1.3. Safety measures

Adverse Events and device deficiencies Ocular and systemic AEs will be collected by the investigator (or authorised assessor/delegate) at each visit.

In case of appearance of a new clinically significant sign or symptom, it should be reported as an AE or SAE.

In case of clinically significant worsening of a pre-existing sign or symptom, it should be reported as an AE or SAE.

The handling of AEs is detailed in **Section 14**.

DD will be also collected.

- Ocular Symptoms Upon Instillation,

The severity of ocular symptoms upon instillation will be assessed by the patient.

“Since the last visit, have you felt any unusual ocular sensation immediately after study treatment instillation (s)?

The following symptoms will be evaluated:

- Burning/Irritation
- Stinging/Eye Pain
- Itching/pruritus
- Eye dryness feeling
- Foreign body sensation
-

Severity will be assessed based on a 4-point scale:

- 0 = Absent,
- 1 = Present but not disturbing,
- 2 = Disturbing
- 3 = Very disturbing.

The translation of these terms will be provided to the site.

- Visual Acuity

Far (BCVA) will be assessed in each eye using the same chart throughout the study. It can be expressed using units as /10, decimal notation, MAR, logMAR, EDTRS or Snellen notation. It will be analysed after conversion in LogMar. [REDACTED]).

- Ocular Tolerance Assessment by the investigator

The investigator has to answer to the following question in local language:

“How do you consider the IMD ocular tolerance?

- Very satisfactory
- Satisfactory
- Not very satisfactory
- Unsatisfactory”

- Ocular Tolerance Assessment by the Patient

The investigator has to ask the patient the following question in local language:

“How do you consider the study treatment ocular tolerance?

- Very satisfactory
- Satisfactory
- Not very satisfactory
- Unsatisfactory”

- Treatment Compliance Evaluation

Patient will return all investigational products (IMDs and Hydrabak®), whether used or unused.

For Hydrabak and IMD (T2769 or Vismed® Multi), the patient will also have to report information about his/her compliance on a paper patient diary during the treatment period. Each day the patient will enter the date and number of instillations* per day. Moreover, it will be asked to add the date and hour of last instillation before the beginning of each study visit.

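### At Visits 3 and 4 five patient items about the product precede the primary Oxford grade in the masked role's block, and no visible rule keeps the grader from asking or hearing them

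*Protocol*

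**What the plan says.** Protocol 6.1.4 prescribes the sequence at the final visit: "Visit#4 will consist of the following procedures and examinations to be done according to the following order and in each eye". Visit 3 carries the same instruction. The clinical block at Visit 4 is assigned as follows: "By the masked investigator (the same as the screening visit) or delegate for selected tasks". Delegation is permitted, not required. For the slit lamp at Visit 4 the rule is "Examination must be performed by the same masked person for all visits and using the same slit lamp"; Visit 3 has an equivalent footnote that also allows a delegate.

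The five items sit under the eCRF part of that block at both visits. Sections 6.4.1.2 and 6.4.1.3 say the following about how they are collected:

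- Ocular tolerance, listed in 6.1.4 as "Assessment of the ocular tolerance by the patient": "The investigator has to ask the patient the following question in local language".
- Global satisfaction: "The patient has to answer to the questionnaire in local language".
- Satisfaction with the bottle: "The patient has to answer to this question in local language".
- Symptoms upon instillation: "The severity of ocular symptoms upon instillation will be assessed by the patient". The Visit 4 list also calls this a questionnaire.
- Soothing sensation: the patient is asked, in the passive, with no questioner named.

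On masking, protocol 6.1.1 explains that a double-masked design is ruled out by the different commercial packaging. Sections 6.1.2.2 and 6.1.2.3 provide identical cartons, keep returned product away from the masked investigator, and have site staff train patients not to reveal product characteristics during visits or when discussing adverse events or device deficiencies. SAP 2.2.2 repeats the masking text, without the patient training, and adds no further rule.

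**The concern.** The Oxford 0-15 total is a clinician's judgement, and the design depends on a grader who does not know the arm. The protocol treats the container as the unmasking hazard, since that is why patients are unmasked and why returned bottles go to someone else. Yet the grader's own block has the patient rate the bottle, the comfort of the drops and their tolerance shortly before staining is graded. A patient answering aloud may add a remark that identifies the product.

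Because one person is meant to examine the patient throughout, something heard at Visit 3 could reach both the D15 and D36 grades, and both enter the MMRM (protocol 7.2.1). A grader who learns or guesses the arm could shift the T2769 minus Vismed Multi difference that is compared with the 2-point margin. The visible text of protocol 7.9 describes no check of whether masking held, so a breach could go unnoticed.

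**Working it through.** The plan gives no figure to reproduce here, so the check is of the text.

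**1. Order.** I counted each line of the Visit 3 and Visit 4 lists in protocol 6.1.4, taking hyperaemia, TBUT and Oxford as separate lines.

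| Item | Visit 3 | Visit 4 |
|---|---|---|
| Symptoms upon instillation | 3 | 3 |
| Soothing | 5 | 5 |
| Bottle satisfaction | 6 | 6 |
| Global satisfaction | 7 | 7 |
| Tolerance by the patient | 8 | 8 |
| Oxford grade | 14 | 15 |

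The Oxford grade is one place later at Visit 4 because visual acuity is added. All 5 items precede it at both visits. A premature discontinuation visit repeats the final-visit procedures, so the same order applies there.

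**2. Who asks.** The investigator is named for 1 item (tolerance) and nobody for the other 4. For global satisfaction and instillation symptoms the word *questionnaire* is compatible with the patient filling in a form. Two places point away from paper without settling it. In 6.1.4 OSDI and VAS come under the paper CRF while the five items come under the eCRF. In 6.5.1 the list of paper-collected assessments covers run-in and IMD instillations, OSDI and VAS only. Where an answer is recorded does not show who asked the question.

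**3. Who grades.** The same masked investigator or delegate. The delegate option covers questioning and examination alike, so it allows the two tasks to be separated but does not require it. Section 6.4 likewise gives all procedures to the same masked investigator or delegate.

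**4. Safeguards against this route.** Identical cartons and the separate handling of returned product deal with what the investigator sees. Only the patient training deals with what the investigator hears. It covers product characteristics, and it sits awkwardly beside a question about the bottle.

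**5. How a remark could reveal the arm.** Protocol 2.3.1 supplies both the run-in Hydrabak and T2769 in ABAK bottles. A patient who says that the bottle is the same as before would point to T2769, provided the comparator's bottle is not of that type. This is an inference: the visible text describes the Vismed Multi container only as multi-dose, in packaging that differs.

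**6. Size.** The documents give neither the frequency of such remarks nor the size or direction of any resulting shift in grading, so no effect on the estimate or the error rate can be calculated.

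**The case against.** The strongest reply is that the route is already covered. The items are closed ratings that say little about the arm, so the opening is a stray remark, and patients are trained not to make one. The same training is relied on for the adverse-event and device-deficiency conversation, which is more open-ended. Diary review and compliance questioning also precede the grade. The investigator manual, said in 6.4 to describe all procedures precisely, may already name the questioner.

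Much of this stands. The training is a real, partial safeguard, and the other conversations remain possible routes. Three things are left. At each visit the adverse-event conversation follows that visit's Oxford grade, whereas the five items precede it. One of the five asks directly about the container that differs between arms. And the tolerance instruction, followed as written, can have the grader question an unmasked patient about the product just before grading.

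A reader might infer that the grader must ask all five items. The text says this for one item only, and of the investigator, who need not be the grader at every site. A reader might also infer that the Visit 3 answers should be withheld from the investigator until D36. The documents do not support that step. Section 6.4.1.3 lists instillation symptoms and patient tolerance as safety measures, the investigator assesses adverse events and is responsible for punctual e-CRF completion, and the ratings themselves reveal little.

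**Conclusion.** The point holds as an avoidable opportunity for unmasking at the primary endpoint, of unknown size. It should be corrected, with medium confidence. Its scope is five items at both post-baseline visits and at a premature discontinuation visit, with the investigator named as questioner for one.

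A reader might go further and conclude that the grader is unmasked, that the non-inferiority comparison is biased, or that the type I error is inflated. The documents support none of these. They show that the opening exists, not that it is used, and any error rate would only restate an assumed shift and standard deviation.

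The conclusion assumes that neither the investigator manual nor Table 2 separates the questioner from the grader. If either does, what remains is to bring that rule into the protocol and align the tolerance instruction with it.

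**What to change.** In protocol 6.1.4, for Visits 3 and 4 and the premature discontinuation visit, require one of two arrangements:

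- the patient completes the five items on paper, alongside OSDI and VAS, before the examination; or
- an existing site delegate who does not grade the Oxford score asks them.

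In either case, do not show the answers to the grader until that visit's Oxford grade is recorded. Amend 6.4.1.3 so that the grader does not ask the tolerance question, and add the five items to the paper list in 6.5.1 if the paper route is chosen.

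After that visit's grade the answers go to the investigator as now. Adverse-event reporting already comes after the Oxford grade in the prescribed order, so adverse-event assessment, safety oversight and e-CRF sign-off are unchanged. The items also keep their place ahead of fluorescein and the Schirmer test.

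The cost is a small protocol and CRF change, one more paper form or some of a delegate's time, and brief retraining; no extra staff are needed. The change does not close every route. Diary review, compliance questioning and the adverse-event and device-deficiency conversation would still rely on the patient training alone.

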6.1.6 Procedures for the Replacement of Patients

The number of randomised patients will be followed in order to obtain at least 226 evaluable patients in the FAS population.

6.1.7 Investigation Sites

Patients are to be enrolled in approximately 40 investigational sites in 9 countries.

The Sponsor will maintain an updated list of Principal investigators and investigation sites, separately from this CIP, throughout the duration of the clinical investigation. The definitive list will be provided with the CIR.

6.1.8 Definition of Completion of the Clinical Investigation

The clinical investigation completion is defined with the last visit of the last patient.

In the case of early termination of the clinical investigation (see Section 16.2), the date of the early termination shall be deemed to be the date of the clinical investigation completion.

¹ If a safety onsite visit is still not possible, the follow-up will be done by phone and the patient is asked to return the used and unused investigation products later, when the situation improves or the pickup of the IMD directly from the patient will be organised. The compliance will be checked with the number of the returned used and unused IMD.

6.2 IMD(S) AND COMPARATOR(S)

6.2.1 Description of the Exposure to the IMD

IMD will be administered by the patient every day for 36 + 3 days, one drop in each eye 3 to 6 times daily into the lower conjunctival sac of each eye.

No IMD instillation at least 2 hours before Visit#3 and 4. However, the first instillation can be done any time after the patient has completed the randomisation visit.

There will be two treatment groups:

- T2769 (test device)
- Vismed® Multi (reference device)

A detailed description of T2769 and of Vismed® Multi is available in **Section 2**.

6.2.2 List of any Other Medical Device or Medication to be Used during the Clinical Investigation

Run-in Treatment/Wash-out Treatment

Once all screening criteria have been checked, the patient will receive a box containing 1 bottle of Hydrabak® treatment for the run-in period between Day-10/-7 to Day 1. 1 drop in each eye 3 to 6 times daily

Hydrabak® is an unpreserved NaCl 0.9% ophthalmic solution supplied in a 10 ml multidose ABAK® system bottle. Hydrabak® will be provided by Laboratoires Théa.

Table 6 Run-in Medical Device Sodium Chloride (Hydrabak®)

Ingredient	Function	Percentage formula (g/100 mL)
Sodium Chloride	Isotonising agent	0.900
Disodium phosphate rate	pH Buffer	0.317%
Sodium dihydrogen phosphate	pH Buffer	0.067%
Water for injections	Vehicle	Ad 100 mL

Batch number and expiration dates will be specified on the packaging.

Auxiliary Products

An auxiliary product is defined as a product used on site for the needs of a clinical investigation as described in the CIP, but not as an IMD.

Fluorescein Faure 0.5% unidoses: one drop will be instilled in the upper bulbar conjunctiva of each eye by the investigator at each visit to perform the slit lamp examination: TBUT and Corneal staining with Oxford 0-15 grading scheme. This staining is assessed with a yellow filter.

Schirmer-Plus: While the patient looks upwards, the lower lid will be drawn gently downwards and temporally. The rounded bent end of a sterile Schirmer test strip will be hooked in the lower conjunctival sac over the temporal one-third of the lower eyelid margin. After five minutes, the moistened paper is removed and the length of the tear absorption on the strip will be measured (in millimeters).

6.2.3 Number of IMD to be Used, Together with a Justification

6.2.4 Justification

During the investigation, each patient will receive 1 bottle of Hydrabak® and the IMD (4 bottles of T2769 or of Vismed® Multi) to cover run-in and active treatment period.

6.3 PATIENTS

6.3.1 Inclusion Criteria

- *Screening Visit*

Patient fulfilling all of the following criteria will be eligible at Screening Visit:

- 1.1. Informed consent signed and dated.
- 1.2. Female or male aged ≥ 18 years old.
- 1.3. Known DES requiring artificial tears for at least the last 3 months prior to screening visit.

- *Randomisation Visit*

Patient fulfilling all of the following criteria will be eligible at Randomisation Visit:

- 1.6. Diagnosis of moderate to severe dry eye syndrome defined by OSDI Score ≥ 23 .
- 1.7. Ocular discomfort evaluated by VAS ≥ 40 mm.

6.3.2 Exclusion Criteria

Patient will NOT be eligible if ONE OR MORE of the following criteria is met at both screening and inclusion visits

Ophthalmic Exclusion Criteria in AT LEAST ONE EYE [2.1]

- 2.1.1 Far BCVA $\geq +0.7$ LogMar (e.g., ≤ 0.2 in decimal value or $\leq 20/100$ Snellen equivalent or ≤ 50 ETDRS letters).
- 2.1.2 Severe blepharitis according to the judgment of the investigator
- 2.1.3 Severe Dry Eye associated with at least one of the following diseases/symptoms:
 - Ocular rosacea
 - Pterygium
 - Eyelid malposition
 - Corneal dystrophy
 - Ocular neoplasia
 - Filamentous keratitis
 - Corneal neovascularisation
 - Orbital radiotherapy
 - Cataract
 - Retinal disease.

Specific Exclusion Criteria Regarding Childbearing Potential Women [2.3]

- 2.3.1 Pregnancy or breast-feeding.
- 2.3.2 Childbearing potential woman neither surgically sterilized nor using an adequate contraception as oral contraceptive, intra-uterine device, subcutaneous contraceptive implant, vaginal ring, patch.

Exclusion Criteria Related to General Conditions [2.4]

- 2.4.1 Alcohol addiction and heavy smoker according to investigator's judgement.
- 2.4.2 Inability of patient to understand the investigation procedures or to give informed consent.
- 2.4.3 Non-compliant patient (e.g., not willing to attend a visit or completing the self-questionnaire; way of life interfering with compliance).
- 2.4.4 Participation in this investigation at the same time as another clinical investigation/study.
- 2.4.5 Participation in this investigation within the exclusion period of a previous study/investigation with a minimum of one month.
- 2.4.6 Patient previously included in this investigation.
- 2.4.7 Patient being institutionalised because of legal or regulatory order, inmate of psychiatric wards, prison or state institutions, or employee of the investigation sites or of the Sponsor's company.
- 2.4.8 Patient not covered by the government health care scheme of the country in which he/she is living (if applicable).
- 2.4.9 Patient under guardianship/ward of court.

Exclusion criteria related to previous and concomitant treatments (medications/non-medicinal therapies/procedures) [2.5]

- 2.5.1 Patient with previous, current or anticipated prohibited listed treatment (or prohibited modification of treatment regimen).

The prohibited treatments (or prohibited modifications of treatment regimen) and their periods of use prohibition are listed in the following table.

Table 7 Prohibited treatments (medications/non-medicinal therapies/procedures)

CONCOMITANT MEDICATIONS/NON-MEDICINAL TREATMENTS NOT ALLOWED BEFORE AND DURING THE INVESTIGATION				
Before the screening visit (Before Day 1-10/Day 1-7)			Run-in period (From Day 1-10/Day 1-7 to Day 1)	After inclusion (Day 1 to Day 36)
12 months	3 months	1 month	Run-in period	Treatment period
Cataract or ocular surgery				
Isotretinoin, cyclosporine, tacrolimus, sirolimus, pimecrolimus And others immune-suppressive medications Topical corticoids and topical antihistaminics Lachrymal plugs				
Any change in systemic medication Contact lenses Antihistaminic and steroid systemic medication				
Any ocular medication except Hydrabak®				
				Any ocular medication including artificial tears except IMD

